## **4.5.2 Secondary Efficacy Endpoints**

Type I error for secondary endpoints is controlled through a hierarchical testing framework. The  $\alpha$  level is 0.05. Following the two statistical comparisons described in Section 4.5.1 for the primary endpoint (Arm A versus Arm Ccontrol and Arm B versus Arm Ccontrol) the secondary endpoints are included in the hierarchy in the following order:

- A versus C randomized comparison: all bleeds
- B versus C randomized comparison: all bleeds
- A versus C randomized comparison: treated joint bleeds
- B versus C randomized comparison: treated joint bleeds
- A versus C randomized comparison: treated spontaneous bleeds
- B versus C randomized comparison: treated spontaneous bleeds
- A versus C randomized comparison: Haem-A-QoL physical health at 24 weeks
- B versus C randomized comparison: Haem-A-QoL physical health at 24 weeks

### **4.5.2.1 All Bleeds**

The definition of all bleeds is described in Section 2.3.2.1. The analysis methodology is the NB regression model or the Van Elteren test, as described for the primary endpoint in Section 4.5.1.

### **4.5.2.2 Treated Spontaneous Bleeds**

The definition of treated spontaneous bleeds is described in Section 2.3.2.2. The analysis methodology is the NB regression model or the Van Elteren test, the same as for the primary endpoint.

### **4.5.2.3 Treated Joint Bleeds**

The definition of treated joint bleeds is described in Section 2.3.2.3. The analysis methodology is the NB regression model or the Van Elteren test, the same as for the primary endpoint.

### **4.5.2.4 Haem-A-QoL at 24 Weeks**

The physical health subscore of the Haem-A-QoL at 24 weeks will be analyzed using analysis of variance (ANCOVA). The model will include the treatment group together

with the baseline score and treatment by baseline interaction as covariates. As for the primary analysis, a global approach with a 3-level categorical effect for treatment (1.5 mg/kg/wk, 6 mg/kg/4wks, or no prophylaxis) will be produced for the comparisons of Arm A versus Arm C and Arm B versus Arm C.

#### **4.5.2.5 Secondary Efficacy Endpoints Not Included in the Hierarchy**

Treated target joint bleeds (defined according to Section 2.3.2.4) on emicizumab will be compared with no prophylaxis and will be analyzed using the same methodology as for the primary endpoint (i.e., using the NB regression model or the Van Elteren test).

The Haem-A-QoL total score, the EQ-5D-5L index utility score based on the U.K. value set, and the VAS at 24 weeks will be analyzed using the same analysis methodology as the Haem-A-QoL physical health subscore (i.e., via ANCOVA).

Only a descriptive summary of the Haemo-QoL-SF will be provided because of the small number of adolescents randomized to the study.

Given the small number of NIS episodic patients that were randomized to Arm A or B, the change in number of treated bleeds and all bleeds will be listed only.

#### **4.5.3 Exploratory Efficacy Endpoints**

All bleeds will be characterized descriptively, including the type, location, and cause of bleed (surgery/procedure, traumatic, spontaneous). Bleed rates for spontaneous and traumatic bleeds will be calculated.

For EQ-5D-5L, Haem-A-QoL, and Haemo-QoL-SF, exploratory analyses include descriptive analyses of change from baseline and between group comparisons over time for each individual subscale and the overall score. In addition, a paired t-test will be conducted to compare the 24-week with the baseline score for the EQ-5D-5L and Haem-A-QoL questionnaires by treatment arm separately. Due to the limited number of adolescent patients, paired t-tests will not be conducted on the Haemo-QoL-SF scales. For EQ-5D-5L and Haem-A-QoL, the number of patients who reported a clinically meaningful change from baseline to Week 24 will be reported. For EQ-VAS, a meaningful change is 7 points and for the index scale it is 0.07 points (Walters et al. 2005; Pickard et al. 2007). For Haem-A-QoL a meaningful change is 7 points for the total score and 10 points for the physical health score (Wyrwich et al. 2015).

The number of days away from school/work and days hospitalized will be presented by treatment arm using descriptive statistics and 95% CIs.

#### **4.5.4 Sensitivity Analyses**

The sensitivity analyses will include different methods to define bleeds or eligible bleed data and different statistical models.

Different ways to define bleeds or eligible bleed data for A versus C and B versus C randomized comparisons:

- Include all bleeds recorded by patients in the electronic patient-reported outcomes device (i.e., without the 72-hour rule)
- Include treated joint bleeds defined as treated bleeds where the bleed type is “joint,” regardless whether any symptoms have been observed
- Include only patients who received at least 12 weeks of emicizumab treatment (if needed)
- Count days when treatment for bleeds was administered instead of the bleeds themselves
- Include only the first 24 weeks of efficacy period in the analysis. Patients who withdraw from study treatment are included up to the point of study treatment withdrawal.

Different statistical models for the bleed rate:

- An alternative NB modeling approach (using the GENMOD procedure) for the primary endpoint in which the A versus C and B versus C randomized comparisons are tested using separate models, including in the first model only the data for patients randomized into arms A and C and in the second model only the data for patients randomized into arms B and C.
- Analysis of variance (ANCOVA)
- Van Elteren test (calculated ABR)

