**Figure 1 Study Schema for Study YO39309**

BR = bleed rate; mo = month.

The primary efficacy analysis, defined as comparing the number of bleeds over time for patients randomized to receive prophylactic emicizumab versus no prophylaxis will be conducted after reaching the clinical cutoff, which occurs at the earliest timepoint when all randomized patients (Arms A, B, and C) have either completed 24 weeks in the study or discontinued from the study.

To obtain additional safety and efficacy data on emicizumab, patients who are randomized to the no prophylaxis arm (control arm, Arm Ccontrol) will have the opportunity to switch after 24 weeks to receive emicizumab prophylaxis at the Arm B dosing regimen (emicizumab prophylaxis at 3 mg/kg QW subcutaneously for 4 weeks, followed by 6 mg/kg Q4W). For clarity, Arm C patients during the no prophylaxis period are designated Ccontrol; whereas, after switch to emicizumab they are designated Arm Cemi. After completing at least 24 weeks of treatment with prophylactic emicizumab, patients who receive emicizumab prophylaxis (Arms A, B, or Arm Cemi after treatment switch) and derive clinical benefit will be allowed to continue emicizumab until marketing authorization as part of this study or a separate extension study, as long as they continue to derive clinical benefit and emicizumab is still in clinical development.

Those who are well controlled after 24 weeks on emicizumab (< 2 spontaneous and clinically significant bleeds) will continue treatment on their assigned emicizumab regimen; whereas, those who experience suboptimal control ( $\geq 2$  spontaneous and

clinically significant bleeds) will have the option to escalate to 3 mg/kg QW after approval from the Medical Monitor.

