## **2.2           COLLECTION OF PATIENT-REPORTED DATA**

### **2.2.1       Collection of Bleed and Medication Data**

Bleed and medication data are collected through an electronic bleed and medication questionnaire (BMQ), which was developed by the Sponsor given that no standard questionnaire for collection of these data exists.

The BMQ was developed as a patient-reported measure of bleeding episodes (including start date and time, reason, type, location, and symptoms of bleeds) and hemophilia-related medication use (i.e. start date and time, reason, type, and dose of injection).

To capture bleed data, emicizumab use, and other hemophilia medication use during study treatment, patients will complete the BMQ on a handheld device that will be provided to them during the Week 1 visit at the study site. This device will remain with the patient for the duration of the study to enter bleed and medication data as soon as bleeding event occurs. In the event of no bleed or medication use, the patient should complete the questionnaire at least weekly at a minimum. In case a patient did not experience any bleeds or administer any treatments for a week, the patient is asked to log into the device and fill in the questionnaire to confirm this. These weekly entries, in addition to the bleeds and medication entries, can also be used to assess compliance. Of note, the patient is able to enter bleeds and medications for the past 8 days, including the day the entries are made. This retrospective data entry window was considered acceptable in terms of recall bias and was added in order to optimize the completeness of data collection.

Patients who withdraw from emicizumab treatment will continue to record bleeds and hemophilia medication administration until they complete the safety follow-up visit.

The patient is able to edit and delete bleeds and medications for 24 hours after they are entered. Furthermore, the investigator and patient are instructed to review the data together at every clinic visit. If the patient has been unable to enter data for any reason, the investigator is able to do so using a data clarification request (DCR; not subject to the previous 8-day data entry window). Note, the symptoms of joint and muscle bleeds are not collected in this case because the patient may not be able to reliably remember them. In addition, the investigator is able to request a change be made to the vendor's database by submitting a DCR.

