#### **2.3.1.1 Efficacy Period**

The start of the efficacy period for each individual patient is defined as the first day when there is data in the BMQ. For patients starting the study on emicizumab (Arms A and B) this is expected to coincide with the Week 1 visit, and the day of their first emicizumab dose. For patients who do not start the study on emicizumab (Arm C), the start of the efficacy period should coincide with the Week 1 visit.

Of note, the first day when there is data in the BMQ, includes the first day for which data is reported via the handheld device, a DCR, or the day of device activation.

A second efficacy period is defined for patients in Arm C who switch to emicizumab starting on the day of their first emicizumab dose.

For patients randomized or enrolled on emicizumab, the end of the efficacy period is defined as the date of the clinical cutoff or the date of withdrawal from the initial study period (i.e., treatment phase according to eCRF), whichever is earlier. For patients randomized to no prophylaxis (Arm C), the end of the first efficacy period is defined as the day before the first emicizumab dose or the date of withdrawal from the initial study period (i.e., treatment phase according to eCRF) or the date of the clinical cutoff if neither of the aforementioned events has taken place. For patients whose dose is up-titrated, the efficacy period on the initial dose (the initial period for patients randomized to Arms A and B; the second efficacy period, starting at first emicizumab

dose for patients randomized to Arm C) ends 1 day prior to the first day on the up-titrated dose.

For patients who withdraw from the study before reaching the Week 1 visit, the duration of the efficacy period is set to 1 day, and it starts and ends on the same day of randomization/enrollment.

For patients whose dose is up-titrated, the bleeds on the up-titrated dose are analyzed separately. The efficacy period on a given up-titrated dose (second efficacy period for patients randomized to Arms A and B; third efficacy period for patient randomized to Arm C) starts with the first day on this dose and ends on the day of the clinical cutoff or the date of withdrawal.

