## 4. **STATISTICAL METHODS**

### 4.1 **OUTPUT LAYOUTS**

The key output layouts are designed to address the study objectives in a flexible manner and provide an overall view of the efficacy and safety of emicizumab. In particular, patients in Arm C are allowed to switch to receive emicizumab after the first 24 weeks in the study, yielding two “study periods” (i.e., when they receive no prophylaxis for the first 24 weeks [no prophylaxis period, designated Arm Ccontrol] and emicizumab prophylaxis thereafter [emicizumab period, designated Arm Cemi]). These two periods are analyzed separately, and either period can be displayed on outputs together with the other treatment arms.

The three key output layouts are:

- **Randomized patients:** comparison of either emicizumab 1.5 mg/kg/wk (Arm A) versus no prophylaxis (control arm [Arm Ccontrol]) prior to switch to emicizumab) or emicizumab 6 mg/kg/4wks (Arm B) versus no prophylaxis (Arm Ccontrol), within a single output produced for all comparisons involving arms A, B, and C prior to switch (Arm A versus Arm Ccontrol and Arm B versus Arm Ccontrol); these outputs form the core set of the efficacy comparisons and will be supported by a corresponding safety analysis. Randomized patients will be used to describe the baseline characteristics and study conduct
- **All emicizumab patients:** these outputs will provide an overall view of all data collected under emicizumab prophylaxis (including control arm patients after switch [Arm Cemi]) and will include analyses of safety and descriptive efficacy
- **Intra-patient comparisons:** for evaluations of the change in the number of treated bleeds and all bleeds over time compared with the patient’s historical bleed rate, only patients who participated in the NIS BH29768 are included

Of note, patients may be allowed to up-titrate their emicizumab dose as described in Section 2. The data under the new, higher dose are analyzed and reported separately. Additional summaries will be produced for key safety and exposure on all data (i.e., data before and after up-titration). Note, with longer follow-up or in case up-titration occurs more frequently than expected, outputs on all data may form the core analysis and additional summaries will be produced by dose.

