### 4.2 **ANALYSIS POPULATIONS**

#### 4.2.1 **Randomized Population (ITT)**

The randomized population (intent-to-treat [ITT]) is defined as all randomized patients. The ITT population will be the primary analysis population for efficacy. Patients are analyzed according to their randomized treatment arm.

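### The sensitivity analysis requiring at least 12 weeks of emicizumab has no workable rule for Arm C: read literally it leaves no controls, and applied to Arms A and B alone it is no longer like for like

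*SAP*

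**What the plan says.** SAP Section 4.5.4 introduces a group of sensitivity analyses as "Different ways to define bleeds or eligible bleed data for A versus C and B versus C randomized comparisons". One bullet in that group is "Include only patients who received at least 12 weeks of emicizumab treatment (if needed". No Arm C counterpart is given, and nothing says what would make the analysis needed.

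Arm C's exposure in the compared period is fixed elsewhere in the SAP:

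- Section 4.1 describes the control period as "when they receive no prophylaxis for the first 24 weeks" and says that the two Arm C periods are analyzed separately.
- Section 2.3.1.1 says that for Arm C "the end of the first efficacy period is defined as the day before the first emicizumab dose", or withdrawal from the initial study period, or the clinical cutoff if neither has happened.
- Section 2 says that controls "will have the opportunity to switch after 24 weeks to receive emicizumab prophylaxis", so any emicizumab they receive comes later and is optional.

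For the main analysis, Section 4.2.1 states: "The ITT population will be the primary analysis population for efficacy". There is no minimum exposure.

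**The concern.** A sensitivity analysis is there to show whether the primary result survives a reasonable change of method. This one sets an eligibility condition on a drug that one of the two compared groups does not receive while it is being compared. The programmer has to decide what the condition means for Arm C, and the choice determines which patients are analyzed.

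Elsewhere the SAP deals with this. The All Emicizumab Patients population (Section 4.2.2) and the two safety populations (Section 4.2.5) each carry a separate Arm C rule. Section 4.5.4 does not.

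At stake is the value of one supporting analysis. If only the active arms are conditioned on staying on drug, a difference from the primary estimate may reflect who was removed rather than how the drug works. Because the trial is open-label and no trigger is set, both the decision to run the analysis and its reading could be settled with early stopping already known.

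**Working it through.** **Step 1: the possible readings**

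1. *Literal, on the compared period.* Every Arm C patient has 0 weeks of emicizumab, so the comparison is up to 28 patients against 0. No rate ratio exists.
2. *Counting emicizumab after the switch.* A control would have to switch after 24 weeks and stay 12 more: 24 + 12 = 36 weeks before cutoff. Controls would be selected on events after the period being compared. This also conflicts with Sections 2.3.1.1 and 4.1, which close the control period before the first dose and keep the two periods apart.
3. *Arms A and B only.* Patients with under 12 weeks of drug leave the active arms and all 14 planned controls stay. This can be computed and is probably what was meant.

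**Step 2: the plan's own figure, to check the planning inputs**

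The SAP gives no number for this analysis. Its power statement (Section 2.4) is more than 90% with 28 versus 14 patients, ABR 4 versus 18, variance 10 times the mean and 0.5 years of follow-up. On the annual scale the negative binomial dispersion is (10 - 1)/mean: 9/4 = 2.25 and 9/18 = 0.5.

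- SE² = (1/(4 × 0.5) + 2.25)/28 + (1/(18 × 0.5) + 0.5)/14 = 0.0982 + 0.0437 = 0.1419, so SE = 0.377.
- Power = Φ(|ln(4/18)|/0.377 - 1.96) = Φ(2.03) = 97.9%.

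The stated bound is reproduced. With 25 instead of 28 active patients the same formula gives 97.0%, so lost precision is not the issue.

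**Step 3: size of the shift under reading 3**

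The documents give no early-stop rate. Assume that 3 of 28 Arm A patients stop early and that the other 25 have ABR 4 over 38 weeks. The 38 weeks is also assumed; it lies inside the 6 to approximately 12 months of observation in Protocol Section 3.1. After removal, both summaries are 4.00.

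| Assumed stoppers | Person-time rate before removal | Shift | Patient-mean ABR before removal | Shift |
|---|---|---|---|---|
| Week 8, ABR 4 | 4.00 | 0% | 4.00 | 0% |
| Week 8, ABR 18 | (25×38×4 + 3×8×18)/(25×38 + 3×8) = 4232/974 = 4.34 | -8% | (25×4 + 3×18)/28 = 154/28 = 5.50 | -27% |
| 1-day period, no bleed | 3800/(950 + 3/7) = 4.00 | about 0% | (25×4 + 3×0)/28 = 3.57 | +12% |

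The last row uses the rule in Section 2.3.1.1 that a patient who withdraws before the Week 1 visit gets a 1-day efficacy period.

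Against a control ABR of 18, the second row moves the ratio from 4.34/18 = 0.24 to 0.22 (person-time), or from 5.50/18 = 0.31 to 0.22 (patient mean). Neither summary is the planned negative binomial estimate. The patient mean is relevant because Section 4.5.1 also reports a calculated ABR per patient and Section 4.5.4 tests it with Van Elteren.

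**Step 4: a range by simulation**

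Large-sample simulation with assumed early-stop rates of 4%, 7%, 10% and 15%:

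- *Stopping unrelated to bleeding.* The rate ratio stays at 1.00 under no effect and 0.22 under the planning effect.
- *Heaviest bleeders stop (an extreme case), active arms restricted only.* Under no effect, 1.00 becomes about 0.91, 0.86, 0.83 and 0.77. Under the planning effect, 0.22 becomes about 0.17, 0.15, 0.13 and 0.11.
- *Heaviest bleeders stop, same rule in all arms.* Under no effect the ratio returns to about 1.00. Under the planning effect it is about 0.19, 0.17, 0.16 and 0.14. Symmetry removes the false signal under no effect but does not recover the all-patients ratio.

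**The case against.** The strongest defence is that this is a wording gap. No analyst would run a comparison with an empty control arm, and the post-switch reading is ruled out by the SAP itself. That leaves a minimum-exposure restriction on A and B, a familiar supplementary analysis. It is conditional, outside the testing hierarchy of Sections 4.5.1 and 4.5.2, and backed by an ITT primary analysis. The same list has a first-24-weeks analysis that keeps early stoppers up to treatment withdrawal. A symmetric 12-week rule would also select on a post-randomization event.

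Most of this stands, and it is why the point is minor. It does not rescue the bullet: the reading that remains still conditions one side of a randomized comparison on retention and leaves the other side whole. Stating that the rule covers A and B only would remove the ambiguity and keep the asymmetry.

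A reader might go further and infer that the analysis favours emicizumab by construction, because patients who leave before 12 weeks are poor responders. The documents do not support that:

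- The withdrawal reasons in Protocol Section 4.6.1 are not exhaustive, but lack of efficacy is not among those named.
- Section 4.6.2 makes discontinuation mandatory only for pregnancy.
- Suspected loss of efficacy leads to discussion with the Medical Monitor (Section 3.1), not automatic exit.
- From the earlier programme, Section 5.1.2.2 mentions one discontinuation for lack of efficacy among patients with anti-drug antibodies and declining drug levels.

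The 1-day rule shows that the shift can also go against emicizumab.

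**Conclusion.** The bullet is wrong as written. Literally it leaves Arm C empty; on its only workable reading it removes early stoppers from Arms A and B, keeps all controls, and breaks the like-for-like comparison. That conclusion follows from the text and needs no assumption about stopping.

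Direction and size do depend on assumptions. With 3 of 28 stopping at week 8, the Arm A shift runs from 0% to -8% in person-time rate and from 0% to -27% in patient-mean ABR as the stoppers' ABR goes from 4 to 18. With very short bleed-free periods the patient mean moves the other way. Even the unfavourable illustration leaves the ratio to control far below 1.

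A reader might also infer that the primary result is at risk. It is not: the primary test is on all randomized patients, and alpha and power do not depend on this analysis. Severity is minor.

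**What to change.** Replace the bullet with a rule that treats the arms alike: include randomized patients with at least 12 weeks of efficacy period in their assigned arm, for A, B and C. Label the result supplementary and conditional on remaining in the study, since it still selects on a post-randomization event. State in advance when the analysis will be run.

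Otherwise delete the bullet. The first-24-weeks analysis in the same list already limits the observation window without excluding early stoppers. The SAP also has patients who stop emicizumab go on recording bleeds: "Patients who withdraw from emicizumab treatment will continue to record bleeds and hemophilia medication administration until they complete the safety follow-up visit".

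The cost is one line of SAP wording, with no new data and no change to conduct. The small downside is that the criterion becomes time observed rather than drug exposure. If an exposure-based view is wanted, it can be given descriptively for the emicizumab arms without a comparison to Arm C.

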#### **4.5.5 Subgroup Analyses**

Comparative subgroup analyses describing the primary endpoint, treated bleed rate, will be conducted for the randomized portion of the study. In addition, estimated ABR including 95% CI will be calculated for all treatment arms in each subgroup. Note, due to the small sample size, all subgroup analyses will be highly sensitive to variability caused by individual patients and need to be interpreted with caution. No p-values will be calculated.

The pre-specified subgroups are:

- Age: 12- $<18$ ,  $\geq 18$
- Age:  $<65$ ,  $\geq 65$
- Number of bleeds during 24 weeks prior to study entry:  $\leq 9$ ,  $> 9$
- Number of target joints: no target joint, any target joint

Subgroup analyses are subject to having sufficient patients in a subgroup to provide meaningful results.

